After passing an initial prescreening, potential participants will provide informed consent and be administered emailed, phone or videoconference-based screening assessments by trained research staff to assess the above inclusion and exclusion criteria. Participants who qualify after completing all screening assessments will then be sent or provided the study materials. This consists of study medication and self-monitoring equipment, including, as needed, a pregnancy test [for females of childbearing age not using contraception], oxygen saturation monitor, automated blood pressure monitor, and thermometer. We will finalize screening (ie confirming medical stability via oxygen saturation monitor, and vital sign measurement) prior to instructing participants to begin taking study medication, after which point (after taking first dose) they are considered "randomized", consistent with Intention to Treat principles.

Study Design

This study will randomize approximately n=152 participants. This study has an initial double-blind phase (to test the drug's effectiveness) followed by an open-label phase (to provide all participants with exposure to the drug, and allow a taper off of it for those initially taking active drug).

Assignment will be 1:1; (1) Active treatment: start and maintain fluvoxamine 100mg, three times daily. May reduce dose (or start at reduced dose) for tolerability reasons; (2) Control: placebo, three times daily. This drug vs placebo phase will last approximately 15 days and will be followed by an open-label fluvoxamine phase that will typically last 6-7 days but could last up to 15 days: 100mg two times daily for 3 days, then 50mg two times daily for 3 days, then discontinue.

Randomization will be stratified by age (we anticipate: 18-44, 45-54, 55-64 and ≥ 65 years, respectively, to reflect the age distribution of ascending risk for severe symptoms requiring hospitalization (https://www.cdc.gov/mmwr/volumes/69/wr/mm6912e2.htm#F2_down) and sex. Final determination of stratification will be made by the biostatistician ([name]). Stratified randomization schedules will be generated by statistician [name].

After the randomized phase, all participants will be followed for approximately 30 days to collect clinical data (i.e., on hospitalization and other clinical outcomes). Thus, total study participation is approximately 45 days (15 days randomized, 30 days follow-up).

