All enrolled participants will also be sent a longterm follow up survey which asks about persistent COVID 19 symptoms, and a PROMIS scale which asks about functioning and quality of life.

Management: To protect research staff, there will be no face-to-face contact with participants; all interactions will be fully-remote via Zoom videoconference and/or phone/text/email, as well as REDCap surveys pushed out to patients via their smartphones or other devices.

For consented participants who start protocolized treatment we will inform their relevant medical providers, such as a PCP, towards the goal of an informed and collaborative management strategy.

As this is a “prevention of clinical deterioration” study, it is anticipated that a minority (~10-15%) of participants will become hospitalized during the study, and that this will most likely occur during the randomized phase. Research staff under the physician investigators’ supervision will provide support including engagement with participants’ caregivers and physicians to ensure timely medical contact and emergency care (including calling 911).

If a study participant develops a decrease in oxygen saturation to less than 90% on room air on >2 readings, persistent increase in respiratory rate to >30 breaths per minute, persistent increase in Heart Rate to > 120 beats per minute, alteration in mentation, or severe worsening in shortness of breath, the research staff will direct them to seek emergency medical care at the nearest emergency department. If none of the above conditions are met, but the research staff still feel that the participant is unwell, one of the physician investigators will evaluate the participant via phone/telehealth and direct them for further care if needed. When a participant is directed to seek emergency medical care, they will be instructed to use a mask if available, and to identify themselves to EMS or to the Emergency Department staff as having been diagnosed with COVID-19.

Safety Assessments

We will assess for adverse events (including serious adverse events) daily via participant self-report during the first 15 days, and then again at the end of the study.

Outcome Assessments

As this is a prevention (of clinical deterioration) trial, the primary endpoint will be a “time to” clinical worsening analysis. Following the intention to treat principle, all participants who are confirmed to have taken at least one dose of study medication are included in the analyses.

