3. Total symptomatic severity during the 15 days using a continuous scale of each patient's presenting symptoms on a 0-10 Likert scale (0= symptom not present, 10= symptom is very severe). Outcomes will be collected daily, with symptomatic data collected approximately twice daily via the technique of Ecological Momentary Assessment (ie "how bad is your symptom right now?"). The most severe symptom at baseline will be the focus. This data collection and analytic technique (with frequent measurement of the symptom[s] most relevant to the individual patient) should greatly increase precision and power (<https://www.ncbi.nlm.nih.gov/pmc/articles/PMC6524455/>).

Data management and analysis: Data will be collected in REDCap and outcomes will be collected by blinded research staff. The study statistician, [name], will conduct blinded (ie "treatment 1 vs treatment 2") analysis under the supervision of [name]. We may conduct an interim "futility" analysis at approximately n=100 participants. The primary analysis will be survival analysis of the primary outcome (clinical worsening), while secondary endpoints (symptomatic severity) will be examined using appropriate (descriptive, Area Under the Curve (AUC), and trajectory) comparisons.

Sharing of de-identified data from this study will be critical because it will help characterize this patient population and, if positive results, would immediately lead to a potential new treatment for COVID-19. Therefore it is planned that a pre-print of the article along with de-identified data will be posted on a public repository such as arxiv (arxiv.org). This has been standard during the pandemic in order to share results as rapidly as possible.

Additional measurements:

Baseline: vital signs (pulse, blood pressure, temperature), O2 saturation, weight and height, symptoms and symptomatic severity.

Follow-up: daily vital signs, O2 saturation, adverse events (participant self-report).

Risks

Potential risks associated with study assessments

There are no risks associated with any of the assessments.

Potential risks associated with study medication

Fluvoxamine:

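### Daily adverse-event self-report is scheduled only for the 15 blinded days, so the placebo arm's first fluvoxamine and the active arm's taper rest on one retrospective check

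*Combined protocol and SAP*

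**What the plan says.** Safety Assessments is the only place that puts days on adverse-event collection. It asks for reports "daily via participant self-report during the first 15 days, and then again at the end of the study".

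Study Design describes a double-blind phase of about 15 days "followed by an open-label phase (to provide all participants with exposure to the drug, and allow a taper off of it" for those who began on active drug. The blinded phase "will be followed by an open-label fluvoxamine phase that will typically last 6-7 days but could last up to 15 days". The open-label dose is 100 mg twice daily for 3 days, then 50 mg twice daily for 3 days. For later follow-up, the same section says "all participants will be followed for approximately 30 days to collect clinical data (i.e., on hospitalization and other clinical outcomes", and that "total study participation is approximately 45 days (15 days randomized, 30 days follow-up".

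Additional measurements has a Baseline line and a second line that reads "Follow-up: daily vital signs, O2 saturation, adverse events (participant self-report". The second line has no start or end day.

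Under Management there are emergency thresholds. If these are not met but staff still think a participant is unwell, "one of the physician investigators will evaluate the participant via phone/telehealth and direct them for further care if needed". Neither provision is tied to a study day.

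**The concern.** The daily inquiry ends at about the moment when the placebo arm first takes the study drug. Those participants start at 200 mg/day, and the tolerability dose reduction in Study Design is written only for the active arm of the blinded phase. The active arm's step-down from 300 mg/day falls in the same window. If staff follow Safety Assessments as written, a side effect in this period is next asked about at the end of the study, unless it comes to light some other way.

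Two things are at stake. One is timely notice of a tolerability problem in a fully remote trial, where staff learn how participants are mainly through what they report. The other is the completeness of open-label safety data, since mild effects that last a few days are easily forgotten over several weeks. The efficacy comparison is not at stake.

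**Working it through.** **Inputs**

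- Blinded phase: about 15 days (Study Design). With the first dose as Day 1, this is Days 1-15.
- Open-label phase: 6, 7 or at most 15 days, starting about Day 16 (Study Design).
- End of study: no day is given. Study Design's total of about 45 days is taken as Day 45; this is an assumption.
- Arm size: 76 (Power analysis).
- Common side effects: 1-10% each (Potential risks associated with study medication).

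**The plan's own figure.** The 76 per group reproduces as a comparison of two proportions, 20% vs 5%, two-sided alpha 0.05 (sidedness is not stated), 80% power, no continuity correction:

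n = [1.96 × √(2 × 0.125 × 0.875) + 0.8416 × √(0.20 × 0.80 + 0.05 × 0.95)]² / 0.15² = (0.9167 + 0.3834)² / 0.0225 ≈ 75.1, rounded up to 76.

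This point uses 76 only as the size of the placebo arm and has no effect on the calculation.

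**Coverage and delay on the Safety Assessments schedule**

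| Open-label length | Days | Placebo arm: fluvoxamine days with daily inquiry | Active arm: same | Delay from event to Day 45 | Placebo-arm exposure without daily inquiry, full uptake |
|---|---|---|---|---|---|
| 6 days | 16-21 | 0 of 6 | 15/21 = 71% | 45 − 21 = 24 to 45 − 16 = 29 days | 76 × 6 = 456 person-days |
| 7 days | 16-22 | 0 of 7 | 15/22 = 68% | 45 − 22 = 23 to 29 days | 76 × 7 = 532 person-days |
| 15 days | 16-30 | 0 of 15 | 15/30 = 50% | 45 − 30 = 15 to 29 days | 76 × 15 = 1,140 person-days |

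Between the last daily report and a Day 45 check there are 45 − 15 − 1 = 29 days with no scheduled report.

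The person-days are upper bounds, because they assume that all 76 start and finish the open-label phase. Management expects about 10-15% of participants to be hospitalized. If, as an illustration, 15% of the placebo arm never started open label, the 6-day figure would be 0.85 × 456 ≈ 388.

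**Expected events.** 76 × 0.01 = 0.76 to 76 × 0.10 = 7.6 placebo participants per listed common effect. The plan says that its risk profile is for chronic psychiatric use and that short-term risk is likely lower, so these figures probably overstate the numbers.

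**Does the Follow-up line close the gap?** It can be read in two ways.

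- As everything after baseline. It then lists what is measured, and Safety Assessments says when. The two sections agree and the gap stands.
- As the 30 days after the randomized phase, which is how Study Design uses the term, with the word daily governing adverse events as well as vital signs. Collection would then run through the open-label phase and there would be no gap.

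The first reading is the more natural. The line is set against Baseline. On the second reading, Safety Assessments would not need a separate end-of-study assessment. Study Design describes the 30 days in terms of clinical outcomes and does not name adverse events. The daily symptom endpoint in the same part of the plan is also confined to the blinded period: "Total symptomatic severity during the 15 days using a continuous scale".

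**The case against.** The strongest reply is that the plan does not leave these participants unattended. The emergency thresholds and physician review have no Day 15 limit. Participants' own medical providers are told of the treatment, staff engage caregivers and physicians, and Minimizing risk adds oversight by physicians who know the drug class. The later follow-up collects hospitalizations at an unstated frequency, so a serious event need not wait until Day 45. The open-label dose (200 then 100 mg/day) is below the blinded 300 mg/day, use is brief, and the plan expects moderate-to-severe and serious attributable events to be uncommon. Consent pages are not available, so it cannot be said whether participants were told to report side effects on their own initiative.

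All of this stands, and it keeps the point minor. It does not remove the point, because none of these provisions schedules an adverse-event inquiry in the open-label window.

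A reader might infer more than the documents support:

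- That Safety Assessments and Additional measurements contradict each other. They do not clearly do so. The Follow-up line is undated and fits the Safety Assessments schedule on its natural reading.
- That adverse-event collection stops at Day 15. It does not, because the end-of-study check remains. The documents do not say whether onset dates are recorded at either time.
- That a physician check is needed before the first open-label dose. That would be a new procedure, separate from the reporting schedule, and it could delay the active arm's taper.

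**Conclusion.** The point holds as a minor safety improvement. On the only schedule with stated days, none of the placebo arm's fluvoxamine days has a daily adverse-event inquiry, and nor does the active arm's taper. The remaining check looks back about 23-29 days for a typical 6-7 day phase, or 15-29 days for the 15-day maximum.

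These figures rest on three assumptions: a switch at about Day 16, a study end near Day 45, and full open-label uptake for the count of 76 and the person-days. They measure exposure without scheduled inquiry, not harm. The first 15 days of both arms are fully covered, so the blinded safety comparison is intact, and nothing in the primary analysis, alpha or power changes.

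**What to change.** In Safety Assessments, state that the existing daily adverse-event self-report continues through each participant's last open-label dose, and keep the end-of-study check. Under Additional measurements, give the adverse-event item in the Follow-up line the same end day.

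Do not require extra saturation readings for this purpose. Clinical worsening is defined partly by saturation below 92%, and that definition sets no time horizon, so further readings could feed the primary endpoint. Reports of dyspnea alone could not, because the definition also needs low saturation or supplemental oxygen.

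The cost is an edit in two places and about 6-7 more days (up to 15) of a short remote survey, with some added burden and some missed entries. It needs no unblinding and no change to the sample size or the analysis.

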Definition of clinical worsening: Clinical worsening is defined meeting both of the following: (1) presence of dyspnea and/or hospitalization for shortness of breath or pneumonia, plus (2) decrease in O₂ saturation ($<92\%$) on room air and/or supplemental oxygen requirement in order to keep O₂ saturation $>92\%$. A laboratory-confirmed clinical endpoint is consistent with World Health Organization clinical trial recommendations (<https://www.who.int/blueprint/15-01-2020-nfr-bp-wg-clinical-trials-ncov.pdf?ua=1>).

Power analysis: The below table regards the primary endpoint. It assumes 80% power, alpha=0.05, and a 20% rate of progression to serious symptoms in the placebo group. The table shows sample size required based on reduction in that rate in the active (fluvoxamine) group. With total n=152 (76 per group), we would have 80% power to find a statistically significant difference in survival curves (i.e., time to clinical worsening) if the rate of progression with fluvoxamine is only 5% (i.e., a three-quarters reduction in the risk of clinical deterioration). This power calculation is conservative because it does not take into account the potentially improved power gained by stratification, or the enhanced power for Kaplan Meier vs. simple rates; therefore, we are likely to be sufficiently powered for a more modest treatment effect.

Treatment Response	N (each group)
.05	76
.06	90
.07	108
.08	131
.09	160
.10	199

We will also examine the following secondary endpoints:

1. clinical deterioration on a Likert-type scale: (1) moderate severity of illness as defined by O2 saturation <92% but no supplemental oxygen requirement; (2) O2 saturation plus supplemental oxygen requirement; (3) O2 saturation <92% plus hospitalization (related to dyspnea/hypoxia); (4) the above, plus ventilator support requirement; (5) the above, plus ventilator support for at least 3 days; (6) death.

2. clinical deterioration measured by number of days: (1) requiring supplemental oxygen; (2) requiring hospitalization; (3) requiring ventilator support.

These Likert-type assessments are based on our review of current COVID-19 treatment studies.

They will be collected in retrospect via patient or family report and/or medical records.

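### The claim that 76 per group is conservative, and likely enough for a weaker effect, rests on a Kaplan-Meier gain that is absent here and a stratification gain that is never quantified

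*Combined protocol and SAP*

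**What the plan says.** The Power analysis paragraph assumes 80% power, alpha 0.05 and a 20% placebo rate, and states: "With total n=152 (76 per group), we would have 80% power" if the fluvoxamine rate is 5%. The table below it asks for 76, 90, 108, 131, 160 and 199 per group for fluvoxamine rates of 5% to 10%.

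Between the two stands the sentence at issue. It begins "This power calculation is conservative because it does not take into account the potentially improved power gained by stratification" and continues "or the enhanced power for Kaplan Meier vs. simple rates; therefore, we are likely to be sufficiently powered for a more modest treatment effect". Neither gain is given a size.

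Four other statements bear on it:

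- Study Design, follow-up: "This drug vs placebo phase will last approximately 15 days", the same for every participant.
- Study Design, strata: "Randomization will be stratified by age" (four anticipated bands) and by sex, but "Final determination of stratification will be made by the biostatistician".
- Outcome Assessments: "all participants who are confirmed to have taken at least one dose of study medication are included in the analyses".
- Data management and analysis: the primary analysis is described only as a survival analysis. No test is named, and nothing says that the analysis is stratified.

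**The concern.** The sentence presents the Kaplan-Meier gain as a fact. A time-to-event test gains over simple rates when follow-up differs between patients or when event timing differs between arms in the helpful direction. This design has one short common window and at most a 20% event rate, so the risk sets hardly shrink and the log-rank test is close to a comparison of event counts. The second reason, stratification, yields a material gain only if the strata enter the analysis and are strongly prognostic. The plan states neither.

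The design effect is already a three-quarters reduction. A reader told that weaker effects are likely covered, with no limit given, could take a null result as evidence against a moderate benefit that the trial had little chance of detecting.

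**Working it through.** **Inputs from the plan.** Power 80%, alpha 0.05, placebo rate 20%, fluvoxamine rates 5% to 10%, 76 per group, 1:1 allocation, window of about 15 days. Sidedness is not stated; two-sided is inferred because it reproduces the table (one-sided would give 60 per group at 5%). The plan gives no loss rate, event timing or stratum risks, so those below are assumptions.

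**1. The plan's table.** Two-proportion formula with pooled variance under the null, where p̄ is the mean of p1 and p2:

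n = [1.96·√(2p̄(1−p̄)) + 0.8416·√(p1(1−p1) + p2(1−p2))]² / (p1−p2)²

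For 20% vs 5%: p̄ = 0.125, so n = (1.96·√0.21875 + 0.8416·√0.2075)² / 0.15² = (0.9167 + 0.3834)² / 0.0225 = 75.1, rounded up to 76. The other rows give 89.4, 107.3, 130.1, 159.7 and 199.0. All six rows match.

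**2. Kaplan-Meier against simple rates.** Power at 76 per group by the same formula, by exact enumeration of the uncorrected chi-square test, and by simulation of the log-rank test (40,000 trials per row, 15-day window, uniform event times, complete follow-up):

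| Fluvoxamine rate | Table formula | Exact chi-square | Log-rank |
|---|---|---|---|
| 5% | 80.5% | 83.3% | 83.3% |
| 6% | 73.2% | 75.6% | 75.0% |
| 7% | 65.3% | 67.2% | 66.6% |
| 8% | 56.9% | 58.4% | 58.1% |
| 9% | 48.6% | 49.8% | 49.1% |
| 10% | 40.7% | 41.6% | 40.7% |

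The log-rank test gains nothing in any row. Exact power is 80% at a fluvoxamine rate of 5.44%. One caution: Schoenfeld's approximation at 76 per group gives 89% at 5% and 81% at 6%, which could pass for a survival-analysis gain. It is an artefact of an extreme hazard ratio, ln(0.95)/ln(0.80) = 0.23, with few events; Freedman's formula gives 78% and 71%.

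**3. Loss to follow-up (assumed 10% and 25%), power at a 5% rate:**

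| Handling of lost patients in the rate comparison | Log-rank / chi-square, 10% loss | Log-rank / chi-square, 25% loss |
|---|---|---|
| Kept as non-events | 80.9% / 81.1% | 76.9% / 77.1% |
| Dropped only if lost before an event | 80.9% / 80.9% | 76.9% / 76.7% |
| All dropped, even after an event | 80.6% / 78.7% | 77.4% / 71.2% |

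Log-rank has a clear advantage only in the last row. In every row it is below its complete-follow-up power of 83.3%, so loss gives no room for a weaker effect.

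**4. Stratification.** Stratified log-rank test, four strata of 19 per arm, placebo risks averaging 20%, common relative risk, complete follow-up, similar timing:

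| Assumed placebo risks by stratum | Power at 6% | Power at 8% | Power at 10% | 80% power at |
|---|---|---|---|---|
| Equal | 74.6% | 57.6% | 40.5% | 5.4% |
| 10/16/22/32% | 76.4% | 58.7% | 41.8% | 5.5% |
| 6/12/20/42% | 78.3% | 61.4% | 44.3% | 5.8% |
| 5/8/17/50% | 80.8% | 64.7% | 46.7% | 6.1% |

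The gain over the unstratified test on the same data is 0 to 4 points at 6% and about 0 to 7 points at 10%. Unequal strata (30/19/15/12 per arm, risks 8/16/26/49%) give 78.9% at 6% and 44.8% at 10%. Eight strata, for age by sex, give 74-82% and 41-47%. With 10% loss the rate at which power is 80% becomes 5.1% to 5.8%; with 25% loss, 4.7% to 5.3%.

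**5. Event timing.** If all placebo events fell in the first half of the window and all active events in the second, unstratified log-rank would gain 3 to 7 points over simple rates (79.8% at 6%, 48.4% at 10%). In the reverse order it would lose 3 to 7 points (71.7% and 35.2%). Favourable timing combined with the steepest strata reaches 80% at 7.5%; reverse timing with the same strata, 5.3%.

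**6. What the sentence would need.** By the plan's own table, 80% power with 76 per group requires an efficiency gain of 90/76 − 1 = 18% at 6%, 108/76 − 1 = 42% at 7%, 131/76 − 1 = 72% at 8% and 199/76 − 1 = 162% at 10%.

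**The case against.** The strongest defence is that no figure is wrong. The sample size and table are right, the sentence is hedged, and its direction is defensible. The table formula is slightly pessimistic (80.5% against 83.3% at 5%), so 80% power does extend to about 5.4%. With a stratified test and steep strata it reaches about 6%, and with favourable timing as well 7.5%. If a rate comparison threw away every lost patient, log-rank would indeed beat it. The table directly below shows that 6% needs 90 per group and 10% needs 199, so a careful reader would not be misled.

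Much of this stands, and it limits the point. The claim is unsupported rather than impossible, and marginally smaller effects are covered. The margin to 5.4%, however, comes from the approximation in the formula and not from either reason the plan gives. The 6% figure under similar timing depends on an analysis the plan does not name and on stratum risks it does not state. Favourable timing is no more assumed in the plan than the reverse, which costs as much. The advantage over discarding lost patients is measured against a power already reduced by loss. The table does not rescue the sentence: it contradicts it, and the sentence tells the reader to expect better than the table.

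**Conclusion.** The concern holds. With 20% on placebo, two-sided 5% alpha, a common window of about 15 days, complete follow-up and similar event timing, the time-to-event analysis adds no material power. 80% power then reaches a fluvoxamine rate of about 5.4% unstratified, and about 6% with a stratified test and steep assumed stratum risks. At 7% power is about 67%. For a halving of risk (10%) it is about 41%, and at most 47% with the steepest strata tried. Loss to follow-up would lower these figures.

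What is misstated is the power claimed for the primary analysis beyond the design effect. The sample size and table stand. The sentence should be corrected, but nothing in the conduct of the trial depends on it.

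**What to change.** Delete the whole sentence that starts "This power calculation is conservative because it does not take into account the potentially improved power gained by stratification" and put in its place:

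> With 76 per group, 20% on placebo, complete follow-up and similar event timing in both arms, the power of an unstratified log-rank test or a comparison of simple rates is about 83% at a fluvoxamine rate of 5% (80% by the formula used for the table), 75% at 6%, 67% at 7%, 58% at 8%, 49% at 9% and 41% at 10%. The time-to-event analysis adds no material power, and loss to follow-up would lower these figures.

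If a stratification gain is to be claimed, name a log-rank test stratified by the randomization factors as the primary analysis, and state the assumed stratum risks.

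The cost is wording only. Sample size, alpha and endpoint are unchanged and no patients are added. The optional stratified test uses strata already planned for randomization. The price is a less favourable power statement for effects weaker than 20% vs 5%.

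### Levels 3 to 5 of the deterioration scale omit the oxygen-requirement route that the primary endpoint accepts, so some hospitalized survivors can be ranked too low or not at all

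*Combined protocol and SAP*

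**What the plan says.** Under Definition of clinical worsening, the primary endpoint has two parts. The first is dyspnea, or hospitalization for shortness of breath or pneumonia. The second is a saturation below 92% "on room air and/or supplemental oxygen requirement in order to keep O₂ saturation" above 92%. Either form of the second part is enough.

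Secondary endpoint 1 is a six-level scale listed after the power table:

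- Level 1: "1) moderate severity of illness as defined by O2 saturation <92% but no supplemental oxygen requirement".
- Level 2: "2) O2 saturation plus supplemental oxygen requirement". No saturation threshold is printed.
- Levels 3 and 4: "3) O2 saturation <92% plus hospitalization (related to dyspnea/hypoxia); (4) the above, plus ventilator support requirement".
- Levels 5 and 6: "5) the above, plus ventilator support for at least 3 days; (6) death".

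There is no level for a participant who meets none of these. On data collection for the scale, the plan says: "They will be collected in retrospect via patient or family report and/or medical records". The analysis sentence under Data management and analysis reads "secondary endpoints (symptomatic severity) will be examined using appropriate (descriptive, Area Under the Curve (AUC), and trajectory) comparisons"; its parenthesis names only symptomatic severity, and no method is given for the ordinal scale. Outcome Assessments includes in the analyses everyone confirmed to have taken at least one dose.

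**The concern.** The scale is meant to grade the deterioration that the primary endpoint detects, but it uses a narrower hypoxia condition. The primary endpoint accepts a low saturation or an oxygen requirement. Level 3 accepts only a low saturation, and levels 4 and 5 inherit that condition because each adds to the level before it.

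A participant may be given oxygen before any value below 92% is recorded. The Management section makes this possible: it directs participants to emergency care for respiratory rate, heart rate, altered mentation or severe breathlessness, none of which needs a low saturation. If that participant is then admitted or ventilated, the primary endpoint is met but level 3 is not.

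What is at stake is the ordering. An ordinal comparison uses only the ranks, and here a sicker participant can rank below a less sick one. With few events expected, several disputed ranks could change the comparison on this endpoint.

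**Working it through.** **1. The plan's own figure.** Inputs from Power analysis: 20% on placebo, 5% on fluvoxamine, 80% power, alpha 0.05 (sidedness not stated; two-sided reproduces the table), 1:1 allocation. With the pooled-variance formula for two proportions and no continuity correction:

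n = [1.960 × √(2 × 0.125 × 0.875) + 0.842 × √(0.20 × 0.80 + 0.05 × 0.95)]² / (0.15)²

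= (0.917 + 0.383)² / 0.0225 ≈ 75.1, rounded up to 76 per group.

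This matches the plan, and the same formula reproduces the other five rows of the table. Nothing below changes it.

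**2. Expected events.** 76 × 0.20 + 76 × 0.05 = 15.2 + 3.8 = 19.

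**3. Survivors set against the printed levels.** The table gives the highest level met. The last column uses the wording proposed under the fix.

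| Course | Primary criterion 2 | Printed level | Reworded level |
|---|---|---|---|
| Below 92%, no oxygen, not hospitalized | met | 1 | 1 |
| Oxygen, no value below 92%, not hospitalized | met | 2* | 2 |
| Below 92% and oxygen, not hospitalized | met | 2 | 2 |
| Below 92%, no oxygen, hospitalized | met | 3 | 3 |
| Below 92% and oxygen, hospitalized | met | 3 | 3 |
| **Oxygen, no value below 92%, hospitalized** | met | **2 or none*** | 3 |
| **The same, ventilated** | met | **2 or none*** | 4 or 5 |
| Below 92% and oxygen, hospitalized, ventilated | met | 4 or 5 | 4 or 5 |
| Neither below 92% nor oxygen | not met | none | 0 |

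*Level 2 applies if it is read as printed, without a threshold. No level applies if the reader assumes the 92% limit from levels 1 and 3.

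The two bold rows hold the rank inversion: both fall below the participant admitted under 92% without oxygen, who scores 3. Death is level 6 whatever the saturation.

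**4. How many are affected.** The documents do not give the share s of events that fall in the bold rows. As an assumed range, the count is 19 × s: 0 at s = 0, 1.9 at 10%, 4.75 at 25%. The ceiling of 19 would need every event to be a hospitalized survivor on oxygen with no low value on record. The Management section expects about 10–15% of participants to be hospitalized, that is 152 × 0.10 = 15.2 to 152 × 0.15 = 22.8. Hospitalization itself is therefore not the limiting condition; the absence of any recorded value below 92% is.

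**5. Participants with no printed level.** With the planning rates as a proxy, 76 × 0.80 + 76 × 0.95 = 60.8 + 72.2 = 133 of 152 (87.5%). The true number may be lower, because levels 1 and 2 do not require dyspnea and so can include participants who miss the primary endpoint.

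**The case against.** The best defence is that the misplaced group is narrow. Level 3 does not say when the low value must occur. Read as at any time, it would take in most participants who need oxygen to stay above 92%. Oximeters are supplied as needed, saturation is a daily follow-up measure, and hospitalized participants are the ones most likely to have medical records. This stands as a limit on size. It does not remove the defect, because the scale does not state that reading, while the primary endpoint spells out both routes.

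Four stronger readings are tempting, and the documents do not support them:

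- *Every event reached through the oxygen route is mis-ranked.* Non-hospitalized oxygen users fit level 2 as printed, deaths are level 6, and anyone with a low value before or during admission reaches level 3 or above. The primary criterion is and/or, so an oxygen requirement does not exclude a low reading.
- *The scale rests on patient or family recall alone.* The plan also allows medical records.
- *The arms would be compared only among participants who deteriorated, a group selected after randomization.* Nothing says so. The plan includes all dosed participants and names no test for this scale. An implied zero is the natural reading; it is simply not written down.
- *Exactly 133 participants have no score.* That figure is a proxy, for the reason in step 5.

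**Conclusion.** The point holds in a limited form. As printed, levels 3 to 5 give a wrong rank to surviving participants who are hospitalized or ventilated on oxygen with no recorded value below 92%: they meet the primary endpoint but score 2 or nothing. The missing threshold in level 2 makes their score depend on the reader. Their number cannot be derived from the documents and is probably a small part of about 19 events.

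This rests on a literal reading of level 3 and on the planning rates of 20% and 5%. The unwritten zero level is a lesser gap, which most analysts would fill in the same way. A reader might infer that the trial's main result is at risk. It is not: the primary endpoint, its analysis and the sample size do not use this scale.

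**What to change.** Use the primary endpoint's either/or wording in the scale:

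- 0: none of the levels below is met.
- 1: as printed.
- 2: supplemental oxygen required to keep saturation above 92%, without hospitalization.
- 3: room-air saturation below 92% and/or a supplemental oxygen requirement, plus hospitalization related to dyspnea or hypoxia.
- 4: level 3 plus ventilation for under 3 days.
- 5: level 3 plus ventilation for 3 days or more.
- 6: death.

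Level 3 should keep the either/or condition and not drop saturation altogether. Otherwise a participant admitted for dyspnea with normal saturation and no oxygen would score 3 without being a primary event. Because levels 1 and 2 still need no dyspnea, the scale and the primary endpoint will not coincide at the lower end; that is a matter of design, not an error. The level 0 puts all dosed participants into the comparison.

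The observation window and the choice of ordinal test are left to the trial team and are not part of this point.

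The cost is the rewording of one secondary endpoint, with the same data, and it should be settled before unblinding.
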